OXPHOS/Glycolysis (OCR/ECAR; **Figure 3C**). These data demonstrate our ability to measure mTOR activation in small numbers of immune cells from children.

Hypothesis, Specific Aims, and Objectives

In this study, we hypothesize that compared to lean children, circulating CD4⁺T cells from obese children with elevated biomarkers of inflammation will have fewer T_{regs} and will exhibit increased mTOR-driven glycolysis. Metformin treatment will increase T_{regs} and shift the metabolic phenotypes of CD4⁺T cells towards AMPK-driven OXPHOS. We will test these hypotheses by executing the following Specific Aim:

Specific Aim 1. Compare the immune and metabolic phenotypes of circulating CD4⁺T cells between lean children and overweight/obese children.

Hypothesis: circulating CD4⁺T cells from obese children with elevated biomarkers of inflammation will have fewer T_{regs} and will exhibit increased mTOR activation and % glycolysis-derived ATP production as compared to CD4⁺T cells from lean children.

Specific Aim 2. Compare the immune and metabolic phenotypes of circulating CD4⁺T cells between T2D children before and after metformin.

Hypothesis: In obese T2D patients, metformin treatment will increase circulating T_{regs}, as well as AMPK activation and % OXPHOS-derived ATP production in CD4⁺ T cells.

Study Design and Procedures

This study consists of:

1. An observational cross sectional immune and metabolic analysis of several groups of children including lean, overweight/obese, and T2D.
2. A prospective immune and metabolic analysis of newly diagnosed children with T2D or insulin resistance who will be or were recently prescribed metformin as part of their clinical care.

Children with T2D or insulin resistance who will be or were recently prescribed metformin, will be asked to complete two study visits. If completed, the second visit will occur 6 months (+/- 2 weeks) after beginning metformin as part of their clinical care. All other children, will be asked to complete only the first visit.

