Prior to any analyses, endpoints data for each group will be closely inspected for the potential presence of unusual values; effort will be made to conserve all data. Analyses will be carried out in SAS 9.4 (SAS Institute, Cary NC) at the 5% significance level; point and 95% interval estimates will be obtained for relevant metabolic group comparisons. Parametric techniques will be first choice and nonparametric equivalents if assumptions are not met. Special attention will be paid to unequal variances.

The study planned four groups of children: lean, healthy obese/overweight, insulin-resistant obese/overweight, and overweight/obese with T2D. Primary comparison of interest are these three: the average of insulin-resistant and T2D obese children compared to (i) lean children and (ii) healthy obese children; and (iii) lean children compared to healthy obese children. Outcomes important to this aim are proportions of T_{reg} cells among circulating CD4 $^{+}$ T cells and CD4 $^{+}$ T glycoATP and mitoATP production. Initially, we will use a one-factor ANOVA to analyze these outcomes (possibly with suitable transformations). Comparisons of interest will then be made with 0.05 significance level *t*-tests conducted within the ANOVA framework.

The requested sample sizes will provide about 0.80 power for detecting differences in means of size 0.8 SD for comparisons (i) and (ii) and size 0.9 SD for comparison (iii), where SD is the within-group standard deviation (a.k.a., root mean square error from the ANOVA). For proportions of T_{reg} cells – a primary outcome of interest, an estimate of the SD is 2.3 percentage points (ref Table 1 of Arismendi et al.⁴²). So, if the means differ by at least 1.85 percentage points in comparisons (i) & (ii) and by 2.10 percentage points for comparison (iii), we will be able to detect these differences with a reasonably high probability (0.80 or higher).

Ethical Considerations

This study will be conducted in accordance with all applicable government regulations and University of Arkansas for Medical Sciences research policies and procedures. This protocol and any amendments will be submitted and approved by the UAMS Institutional Review Board (IRB) to conduct the study.

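### Are the three primary t-tests conditional on a significant ANOVA F test, so that the stated 0.80 power fails?

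*Combined protocol and SAP*

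**What the plan says.** The protocol and SAP are one document, and only its Data Analysis section deals with this. It defines four groups (lean, healthy overweight/obese, insulin-resistant overweight/obese, overweight/obese with T2D) and names three primary comparisons:

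- (i) the average of the insulin-resistant and T2D groups against lean;
- (ii) the same average against healthy obese;
- (iii) lean against healthy obese.

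The sequence is then "Initially, we will use a one-factor ANOVA to analyze these outcomes", followed by "Comparisons of interest will then be made with 0.05 significance level" t-tests that use the ANOVA's pooled error. On estimation, "point and 95% interval estimates will be obtained for relevant metabolic group comparisons". On size, "The requested sample sizes will provide about 0.80 power for detecting differences in means" of 0.8 SD for (i) and (ii) and 0.9 SD for (iii), where SD is the pooled within-group value. For the Treg proportion, "a primary outcome of interest, an estimate of the SD is 2.3 percentage points", which the plan converts to detectable differences of 1.85 and 2.10 percentage points. No multiplicity adjustment is mentioned, and no role in the decision is given to the overall F test.

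**The concern.** An ANOVA done first with t-tests after it can describe two procedures. In one, the ANOVA only supplies the pooled error and the three planned contrasts are tested in any event. In the other, a significant F on 3 degrees of freedom is required before any contrast is looked at. The text does not exclude the second.

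Three things would be at stake:

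- **Power.** The stated power is that of a single contrast. An F condition can lower it.
- **A choice after the data.** In some mean patterns a contrast is significant and F is not in 6-18% of studies. Without a written rule, the team could decide afterwards whether such a result counts.
- **False positives.** The two procedures differ in the chance that at least one of three tests is significant when nothing differs.

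**Working it through.** **Inputs.** Study Population: about 20 lean, about 40 overweight/obese of whom about 20 are expected to be insulin resistant, and about 20 with T2D. That is 20 in each of four groups, with error df = 80 − 4 = 76. Data Analysis: 0.05 per test, effects of 0.8 SD and 0.9 SD, SD 2.3 percentage points. Two-sided tests are assumed; this fits the 95% intervals, and one-sided tests would give 0.89 and 0.88, which do not match the plan. Equal variances are assumed.

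**Step 1: the plan's own figure, without an F condition.** The standard error of a contrast, in SD units, is √(Σc²/n).

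- (i) and (ii): √[(1 + 0.25 + 0.25)/20] = √0.075 = 0.274. Noncentrality 0.8/0.274 = 2.92. Power from the noncentral t on 76 df: **0.82**.
- (iii): √[(1 + 1)/20] = √0.10 = 0.316. Noncentrality 0.9/0.316 = 2.85. Power: **0.80**.

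In Treg units, 1.85/2.3 = 0.804 SD gives 0.83 and 2.10/2.3 = 0.913 SD gives 0.81. The plan's figures are reproduced.

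**Step 2: power if F had to be significant too.** Power becomes P(|t| > 1.99 and F > 2.72). It depends on all four means, which the document does not give. Simulation with 1,000,000 studies per pattern (means in SD units):

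| Contrast | Lean, healthy obese, insulin-resistant, T2D | No condition | With F condition |
|---|---|---|---|
| (i) | 0, 0, 0.8, 0.8 | 0.82 | 0.77 |
| (i) | 0, 0.4, 0.8, 0.8 | 0.82 | 0.66 |
| (i) | 0, 0.53, 0.8, 0.8 (least favourable) | 0.82 | 0.65 |
| (i) | 0, 0.8, 0.8, 0.8 | 0.82 | 0.69 |
| (i) | 0, 0, 0.4, 1.2 | 0.82 | 0.81 |
| (iii) | 0, 0.9, 0.45, 0.45 (least favourable) | 0.80 | 0.62 |
| (iii) | 0, 0.9, 0.9, 0.9 | 0.80 | 0.74 |
| (iii) | 0, 0.9, 1.7, 1.7 | 0.80 | 0.80 |
| (ii) | 0, 0.9, 1.7, 1.7 | 0.82 | 0.82 |

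Contrast (ii) mirrors (i) when lean and healthy obese swap places. In the least favourable patterns the F noncentrality is only the square of the contrast's own (2.92² = 8.53; 2.846² = 8.10) but is spread over 3 df, so F alone has power 0.66 and 0.63-0.64. Once the means are more spread, the condition costs almost nothing. So contrast size alone guarantees about 0.80 only without a condition, but a condition does not always break the figure.

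**Step 3: false positives, at least one of three tests significant, per outcome.**

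| Means | No condition | With F condition |
|---|---|---|
| all four equal | 12% | 4% |
| insulin-resistant −0.4, T2D +0.4, others 0 | 12% | 10% |
| −0.6, +0.6 | 12% | 12% |
| −0.8, +0.8 | 12% | 12% |

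The lower rate of 4% therefore needs all four means equal. It is not enough that the insulin-resistant/T2D average equals the other two groups.

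**Step 4: which procedure the text describes.** The comparisons are listed beforehand as primary, the sentence saying they will be made carries no condition, the level is fixed per test, intervals are promised for group comparisons, and power is quoted per comparison at values that Step 1 reproduces. The ANOVA comes first because it supplies the error term, and the plan defines its SD as that same quantity. An F condition has to be added by the reader.

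**The case for a change.** The strongest case for a change is that the document nowhere rules out an F condition, that no other analysis section could supply the rule, and that one sentence would remove a choice otherwise open after the data are seen. The stakes are real in plausible patterns: the preliminary PBMC data showed no lean-obese difference, which points to the 0.77 case (though that data set had only two T2D children). All of this is correct as far as it goes. The silence exists and the lower power figures reproduce. But the sentence would only write down what the text and its power figures already convey; it would correct no number and alter no analysis.

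A second argument is that three unadjusted tests on three outcomes should be contained by making the Treg proportion the sole primary outcome, since it alone appears in both the Aim 1 hypothesis and the analysis section and alone has a detectable difference in its own units. That is a separate decision about endpoint hierarchy, and the silence on F does not require it. The textual premise is also thin: Aim 1 predicts that CD4⁺ T cells "will exhibit increased mTOR activation and % glycolysis-derived ATP production", and that percentage is formed from the glycolytic and mitochondrial ATP rates listed in the analysis section. Demoting those rates would remove much of the metabolic half of the hypothesis from the primary analysis, and reasonable statisticians would differ on it.

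**Conclusion.** No change is needed. The plan omits a detail that an analyst would fill correctly from the surrounding text: test the three planned contrasts at 0.05 each, whatever the overall F result, and report them with their 95% intervals. On that reading the stated power holds (0.82 for (i) and (ii), 0.80 for (iii)), given 20 completers per group, equal variances and two-sided tests. The 0.62-0.77 range belongs to a procedure the plan does not describe, and even there only to patterns with equal insulin-resistant and T2D means and the remaining mean at or between the two compared.

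The price of the planned approach is a 12% chance per outcome of at least one significant contrast when all four means are equal. Testing three prespecified contrasts without adjustment is a fair trade-off in an observational study whose results are to serve as preliminary data for a grant application. An explicit statement that the tests do not depend on F and are unadjusted would do no harm, but the soundness of the analysis does not rest on it.

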Figure 2: The ATP production rate assay demonstrates increased % glycolysis-derived ATP production in PBMC from T2D children. Oxygen consumption rate (OCR) (A) and Proton Efflux Rate (PER) (B) are plotted over time in PBMCs from lean, obese (OB) and type 2 diabetic (T2D) children. Injections of Oligomycin (oligo) and Antimycin A (AMA) and Rotenone (ROT) are indicated. (C) Glycolytic ATP production rate (glycoATP) and mitochondrial ATP production rate (mitoATP) are calculated from OCR and PER. (D) % glycolysis and % OXPHOS-derived ATP production are calculated. * $p=0.032$

Methods: Freshly isolated PBMC from lean ($n=8$), obese (OB; $n=11$), and treatment-naive type 2 diabetic (T2D; $n=2$) children were plated at 2.5×10^6 cells/well in RPMI 1640 with 1mM HEPES, 2mM glutamine, 1mM pyruvate and 11mM glucose on poly-D-lysine coated XF96 plates. Plates were centrifuged at 100xg with no brake to adhere cells to well bottoms. After a 30 min incubation in a 37°C non-CO₂ incubator, cells were assayed in a Seahorse XF96.

note regarding this data: 1) these data are from PBMC, a mixed population of cells including monocytes and lymphocytes of various subtypes rather than purified CD4⁺ T cells as proposed in this study; 2) the obese subjects have not been classified as metabolically healthy or unhealthy; 3) the age of the T2D subjects is greater (16.5±0.1 years; mean±SD) than the other groups (lean: 6.8±1.1 years; obese: 7.9±1.4 years). In the studies proposed herein, we will match groups on age and subgroup obese subjects as metabolically healthy and unhealthy based on insulin sensitivity. Further, after measuring high sensitivity CRP (hsCRP), we will compare subjects with hsCRP values in the top quartile to the other groups to determine whether the % glycolysis is higher in CD4⁺T cells from those obese subjects with inflammation.

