to complete the procedure(s). At the first, second, or reattempt visits, participants/parents may be given up to \$20 in ACRI merchandise and/or child-friendly stickers. Food and drinks may be provided during study visits following the fasting blood draw.

Study Population

110 children ages 5-17 years old will be recruited with the goal that approximately 80 subjects stratified across the following groups will complete the study: i) healthy lean (approximately n=20); ii) overweight/obese (approximately n=40, with the anticipation that approximately 20 of these children will be insulin resistant); iii) overweight/obese with T2D and prescribed Metformin (approximately n=20). Every attempt will be made to ensure that the desired number for each group is achieved and groups are balanced with respect to age, sex and ethnicity.

Inclusion Criteria:

- Age 5-17 years, inclusive
- Either healthy lean ($BMI \geq 5^{\text{th}}$ percentile and $< 85^{\text{th}}$ percentile for age/sex) or overweight ($BMI \geq 85^{\text{th}}$ percentile and $< 95^{\text{th}}$) or obese ($BMI \geq 95^{\text{th}}$ percentile for age/sex)
- For those with $BMI \geq 85^{\text{th}}$ percentile for age/sex, parental verbal confirmation that the child had a history of $BMI \geq 85^{\text{th}}$ percentile for age/sex for at least six months prior to study enrollment

OR

- Age 5 years - 17 years 5 months, inclusive
- Either overweight or obese ($BMI \geq 85^{\text{th}}$ percentile for age/sex)
- Parental verbal confirmation that the child had a history of $BMI \geq 85^{\text{th}}$ percentile for age/sex for at least six months prior to study enrollment
- Diagnosed with type 2 diabetes mellitus or insulin resistance
- Prescribed metformin (either not yet taking or began taking within 3 weeks of enrollment)

Exclusion criteria:

- Having an infection (viral, respiratory, gastrointestinal) in the previous 4 weeks
- Genetic or physical conditions impacting mobility over past year as determined by the PI
- Having known chronic illnesses/disorders that may independently affect study outcome measures: type 1 diabetes mellitus, neurologic (e.g. epilepsy), developmental (developmental delay, autism spectrum disorder), endocrine (thyroid, Cushing's), hepatic, autoimmune, cardiac and renal disorders. Also, chronic lung disorders except well controlled asthma that does not require permanent use of inhaled/oral steroids

Title: Immunometabolism in Pediatric Obesity

PI: [name].

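### Do three primary group contrasts, each tested at 0.05, need family-wise error control?

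*Combined protocol and SAP*

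**What the plan says.** All of the following is in the Data Analysis section of the combined protocol and SAP unless noted.

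- Analyses are run "at the 5% significance level", and estimates with 95% intervals are promised for the relevant group comparisons.
- "Primary comparison of interest are these three": the average of the insulin-resistant (IR) and T2D groups against (i) lean and (ii) healthy obese, and (iii) lean against healthy obese.
- The sentence that begins "Outcomes important to this aim are proportions of" Treg cells goes on to add CD4⁺ T-cell glycoATP and mitoATP. Of the three, only the Treg proportion is called "a primary outcome of interest, an estimate of the SD is 2.3 percentage points", and only it has detectable differences in its own units.
- A one-factor ANOVA is fitted first. "Comparisons of interest will then be made with 0.05 significance level" t-tests within that ANOVA. A significant F is not made a condition, and no multiplicity adjustment appears.
- Power is put at about 0.80 for 0.8 SD in (i) and (ii) and 0.9 SD in (iii), or 1.85 and 2.10 percentage points of Treg.
- Study Population plans about 20 lean, 40 overweight/obese ("with the anticipation that approximately 20 of these children will be insulin resistant") and 20 T2D children.

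**The concern.** The plan itself gives three contrasts the label primary, so the family is not a reviewer's invention. Three tests at 0.05 with no rule linking them suggest an inflated chance of some false primary result. If glycoATP and mitoATP also counted as primary there would be nine tests, and the text does not say outright that they do not. The opening ANOVA might look like protection, but the wording does not make it a gate. At stake is whether a reader of the eventual paper could take one significant primary contrast as carrying a 5% error rate when the rate for the set was higher.

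**Working it through.** **Inputs.** Four groups of 20 (the anticipated split), error df = 80 − 4 = 76, α = 0.05 per contrast, Treg SD 2.3 points. Sidedness is not stated; two-sided is assumed, in line with the 95% intervals. M denotes the average of the IR and T2D means, L lean, H healthy obese.

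**1. The plan's own power.** In units of SD²:

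- Var(M − L) = Var(M − H) = 1/20 + 1/40 = 0.075. Noncentrality at 0.8 SD = 0.8/√0.075 = 2.92; power from the noncentral t = 0.822.
- Var(L − H) = 2/20 = 0.10. Noncentrality at 0.9 SD = 0.9/√0.10 = 2.85; power = 0.802.
- In Treg points, 0.8 × 2.3 = 1.84 and 0.9 × 2.3 = 2.07, against the stated 1.85 and 2.10 (rounding).

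The stated power therefore fits unadjusted, ungated tests. It does not prove that reading: with tests gated on the overall F, power also reaches about 0.82 for (i) and 0.80 for (iii) under some patterns of the other means.

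**2. Error for one outcome when L = H = M.** Independent contrasts would give 1 − 0.95³ = 0.143. The actual correlations are 0.025/0.075 = 1/3 between (i) and (ii), and ∓0.05/√(0.075 × 0.10) = ∓0.577 between (i) or (ii) and (iii). Simulation with these correlations and the pooled variance gives 0.120.

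**3. Error for one outcome in every other case.** (M − H) − (M − L) = L − H, so if any two of the nulls hold, the third does too. The number of true nulls is 3, 1 or 0, never 2. Unless all three means are equal, at most one true null is tested, at 0.05. Simulation (200,000 studies each):

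| Pattern | Error for the family |
|---|---|
| L = H, M lower by 0.8 SD | 0.049 |
| Only L different | 0.050 |
| Only H different | 0.050 |

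**4. All three outcomes as one family.** The documents give no correlation between outcomes, so a common value is assumed. With every null true, the chance of at least one false positive in nine tests is about 0.32, 0.28, 0.22, 0.19 and 0.13 at correlation 0, 0.5, 0.8, 0.9 and 0.999. Some correlation between the ATP measures is plausible, since "Glycolytic ATP production rate (glycoATP) and mitochondrial ATP production rate (mitoATP) are calculated from OCR and PER" (Preliminary Data, Figure 2). If instead each outcome had one true null, independence would give 1 − 0.95³ = 0.143.

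**5. What control would cost.**

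| Rule | Error, all null | Power (i)/(ii) at 0.8 SD | Power (iii) at 0.9 SD |
|---|---|---|---|
| As planned | 0.120 | 0.822 | 0.802 |
| Gate on 2-df test of L = H = M | 0.050 | 0.72–0.82 | 0.69–0.80 |
| Gate on overall 3-df F | 0.038 | 0.65–0.82 | 0.62–0.80 |
| Bonferroni, 0.05/3 | at most 0.05 | 0.682 | 0.655 |

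The ranges cover different values of the other group means. The overall F is not a sound gate: with IR and T2D 0.8 SD either side of equal L and H, the gated error is back at 0.120. Restoring 0.80 power under Bonferroni needs 26–27 children per group, or 104–108 completers against about 80 planned.

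**The case for a change.** The strongest case for a change is this. The investigators chose formal 0.05 tests, a primary label and a power calculation, so they should own the error rate of the set. The 12% needs no assumption about outcome correlation. The 2-df gate is a valid closed procedure for exactly these contrasts, is never less powerful than Bonferroni, and needs one extra contrast statement and no extra children. The status of the ATP outcomes is also unclear: Treg percentage is called a primary outcome rather than the only one, and the Aim 1 hypothesis sets glycolysis-derived ATP beside Treg counts.

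The arithmetic stands, and so does the observation that the text neither names a single primary outcome in so many words nor states the role of F. Those are missing details that an analyst fills from the section as written: Treg percentage is the one outcome labelled primary and powered in its own units, and the t-tests are not conditional on F.

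The rest does not force a change. The intended error rate is stated, and it is per comparison. All three contrasts are fixed in advance and intervals are promised, which limits selective emphasis; a gate would not prevent selective reporting in any case. The gate also protects only where all three means are equal, still leaves 9–14% across three outcomes, and is defined only for the pooled-variance analysis, whereas the plan allows nonparametric alternatives and flags unequal variances.

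**Conclusion.** No change is needed; the choice between per-comparison and family-wise control is a trade-off here, not an error. For Treg percentage the unadjusted plan has a 12% chance of some false positive if lean, healthy-obese and average(IR, T2D) means all coincide, and at most 5% otherwise. The nine-test figure, about 13–32% with all nulls true, depends on an assumed between-outcome correlation and on treating all three outcomes as one confirmatory family. Removing the 12% would cost between 0.00 and 0.11 in power with the best gate, taking power below the stated 0.80 under many mean patterns.

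Statisticians differ on adjusting three prespecified contrasts, and the setting favours leaving them alone. Study Design and Procedures describes an observational cross-sectional comparison, and the statement of purpose before Preliminary Data says that the results are to support a later grant application. These figures assume 20 completers in each of four groups, two-sided tests and a common within-group variance.
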